7.9.15 Time to meaningful relief

Time to meaningful relief is the time when the subject experiences relief that is meaningful after the administration of study drug and stops the second stopwatch, irrespective of the first stopwatch. If it is not stopped, time will be censored at the time of the second dose or the first use of rescue medication whichever comes first.

7.9.16 Rescue Medication Use

Total use of rescue medication is the number of times that a subject used rescue medication for pain during the specified time periods (0-24h and 0-48h). The proportion of subjects taking rescue medication for pain during each period will also be presented. A subject taking any amount of rescue medication during the specified period will be counted in this proportion.

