Oxygen saturation will be monitored continuously and the study team will measure all vital signs (blood pressure, heart rate, respiratory rate, and oxygen saturation) at least every 5 minutes until the AE of hypotension or hypoxia as described above is no longer present.

5. If >8 mg i.v. ondansetron is needed within an 8-hour segment and persistent nausea and/or emesis is present.
6. Pain cannot be adequately managed (in the investigator's opinion) by a combination of study drug and rescue medication, or who develop unacceptable side effects during the study, will be discontinued from further study participation.

Pain will be managed according to usual standard of care at the investigator's discretion.

If a subject is withdrawn before completing the study, the reason for withdrawal and the date of discontinuation will be recorded on the appropriate case report form (CRF). Whenever possible and reasonable, the evaluations that were to be conducted at the completion of the study should be performed at the time of premature discontinuation.

If a subject discontinues the study prematurely, pain intensity, pain relief, and the subject's global satisfaction with study treatment should be assessed and recorded immediately before discontinuation.

Withdrawn subjects will not be replaced. If a substantial number of subjects are withdrawn from the study, then the sponsor will evaluate the need for developing replacement criteria.

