Pain will be assessed on an 11-point Numeric Rating Scale (NRS) at Baseline before Time 0. Thereafter, subjects will rate their pain intensity (NRS) and pain relief (on a 5-point categorical scale) and record their assessments in an inpatient subject diary at scheduled times during the 48-hour period after Time 0 (at 2.5, 5, 15, 30, and 45 minutes, and 1, 1.5, 2, 3, 4, 5, 6, 7, 8, 12, 16, 20, 24, 32, 40, and 48 hours) and immediately before each use of rescue analgesia during the Treatment Period. Time to perceptible pain relief and meaningful pain relief will be evaluated using the 2 stopwatch method (after the first dose only). Time to each rescue medication from the prior IP dose will be evaluated. Subjects will complete a subject's global evaluation of the study drug at the end of the Treatment Period (Day 3) before discharge from the study site.

If a subject discontinues the study prematurely, pain intensity, pain relief, and the subject's global satisfaction with study treatment should be assessed and recorded immediately before discontinuation.

Before discharge from the study site on Day 3, study personnel will dispense a prescription for outpatient pain medication (if not already dispensed) and subjects will be given an outpatient subject diary in which they will be instructed to record concomitant medications taken and adverse events (AEs) experienced after discharge. Subjects will also be instructed to return the outpatient subject diary to study personnel at the Follow-up Visit on Day 7 ± 2 days (5 to 9 days after surgery).

The Schedule of Assessments for the study is presented in the Appendix I of this SAP.

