7.3 Handling of Missing Data

7.3.1 Handling of Missing Data for Efficacy Assessments

Use of Rescue Medication: Any pain intensity or pain relief score occurring within 4 hours after a subject has taken rescue medication for pain will be replaced by the last pain intensity or pain relief score prior to that use of rescue medication. If a second rescue medication for pain is used within that 4 hour duration, the pain intensity or pain relief scores from the time of the first rescue medication will be replaced by the assessment prior to the second rescue medication for the next 4

hours. The same method will be employed for a third and subsequent rescue medication.

Missing due to Dropouts: Missing values for pain intensity after a subject drops out of the study will be imputed as follows in the primary analysis:

- For SPID endpoints, the last available SPID (truncated SPID) will be used for analysis (e.g., if a subject dropped out after 32 hours of initiation of treatment, the truncated SPID calculated using timepoints up to 32 hours will be used as the post 32 hour timepoints like 40 hours and 48 hours).
- For TOTPAR endpoints, the last available TOTPAR (truncated TOTPAR) will be used for analysis
- For PID endpoints, the last available pain intensity will be used to impute the missing pain intensity and to calculate the PID

In addition, a sensitivity analysis using 1) missing as missing (i.e., no imputation) for dropouts and 2) multiple imputation will be performed for the primary endpoint to explore the impact of missing data after a subject drops out. The details of the sensitivity analysis are described in [Section 7.4](#).

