7.9.17 Time to First Use of Rescue Medication

Time to first use of rescue medication for pain is defined as the time from Time 0 to the first use of rescue medication. Rescue medications for pain will be identified by the sites on the Concomitant Medications eCRF. If rescue medication for pain is not taken, the time will be censored at the time of the last pain assessment.

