8.2.2.10 Proportion of subjects using rescue medication

The definition of rescue medication use is presented in [Section 7.9.16](#). The proportion of subjects using rescue medication for pain will be analyzed using logistic regression. The logistic regression model will include factors site, treatment and baseline pain intensity.

8.2.2.11 Time to first use of rescue medication (duration of analgesia) following each dose of IP

Time to time to first use of rescue medication will be summarized using Kaplan-Meier methods. Censoring will be applied as described in [Section 7.9.17](#). Treatments will be compared to placebo using a log-rank test which will compare the survival distributions of the treatments.

8.2.2.12 Total use of rescue analgesia over 0 to 24 hours and over 0 to 48 hours

The frequency of use of rescue analgesia will be calculated for each subject over 0 to 24 and 0-48 hours. The differences in total use of rescue analgesia between the treatment groups and placebo will be compared using an analysis of covariance (ANCOVA) model, which will include treatment and site as main effects and baseline pain intensity as the covariate. The last square (LS) mean, standard error (SE) and 95% confidence interval (CI) for each treatment group will be estimated for each time interval 0-24 hours and 0-48 hours. In addition, the mean (LS mean) difference between each treatment and placebo, SE, p-value and the associated 95% CI will also be computed. Descriptive summaries (including mean, SD, median, minimum and maximum) will also be presented by treatment group.

8.2.2.13 NRS pain intensity difference (NRS PID) at each scheduled time point after Time 0

The PID at each scheduled time point will be calculated using the formula specified in [Section 7.9.6](#). The differences in NRS PID between the treatment groups and placebo will be compared using an analysis of covariance (ANCOVA) model, which will include treatment and site as main effects and baseline pain intensity as the covariate. The last square (LS) mean, standard error (SE) and 95%

confidence interval (CI) for each treatment group will be estimated. In addition, the mean (LS mean) difference between each treatment and placebo, SE, p-value and the associated 95% CI will also be computed. Descriptive summaries (including mean, SD, median, minimum and maximum) will also be presented by treatment group.

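### Total rescue use is compared as a raw count with no allowance for hours on study, and the per-dose time to rescue named as an endpoint is never defined in the SAP

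*SAP*

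**What the plan says.** **Rescue count.** SAP 7.9.16: "Total use of rescue medication is the number of times that a subject used rescue medication for pain during the specified time periods". The periods are 0-24 h and 0-48 h. SAP 8.2.2.12 repeats it: "The frequency of use of rescue analgesia will be calculated for each subject over 0 to 24 and 0-48 hours". The comparison is an ANCOVA "which will include treatment and site as main effects and baseline pain intensity as the covariate", with LS mean differences from placebo, p-values and 95% CIs. Protocol 8.5.3.2 asks for the same approach as for the primary endpoint.

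**Withdrawal.** Protocol 3.3 removes subjects whose pain cannot be managed "by a combination of study drug and rescue medication" and passes them to standard of care. They are not replaced, and they stay in the ITT population. SAP 7.3.1 introduces its dropout rules with "Missing values for pain intensity after a subject drops out of the study will be imputed as follows in the primary analysis" and lists rules for SPID, TOTPAR and PID only.

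**Time to rescue.** The endpoint lists (Protocol 8.1.2, SAP 3.1.2) and the heading of SAP 8.2.2.11 refer to first rescue after each dose of investigational product. SAP 2.2, like the protocol synopsis, says: "Time to each rescue medication from the prior IP dose will be evaluated". Protocol 8.5.3.2 also names an average time to rescue after a dose. SAP 8.2.2.11 takes its censoring from SAP 7.9.17, where the time is "defined as the time from Time 0 to the first use of rescue medication", censored at the last pain assessment.

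**The concern.** A count over a fixed window is comparable between subjects only if all are observed for the whole window. Here follow-up can end because of the very thing the endpoint measures: a subject needing frequent rescue and still in pain is withdrawn, and that subject's count freezes. Early treatment failure can then look like modest rescue use, and the ANCOVA has no term to tell the two apart.

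The second problem is a mismatch inside the plan. A programmer following SAP 7.9.17 will produce a valid time from first dose to first rescue. That programmer will not produce the duration of analgesia after each dose, which both documents list as an endpoint, nor the per-dose average in Protocol 8.5.3.2. Time to rescue after fentanyl spray is a secondary objective in the protocol synopsis and SAP 2.1.

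**Working it through.** The plan gives no rescue rate, dropout rate or power figure for these endpoints, so there is no figure of its own to reproduce. Rates below are assumptions; 15 per arm, the 48 h window and the 12 doses are from the documents.

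**1. Illustration for the 48 h count.** Assume 11 placebo completers with 7 uses each, 4 placebo subjects leaving at 8 h after using 0.3 per hour, and an active mean of 5 with no withdrawals. The 0.3 per hour (7.2 per day) lies within the stated daily ceilings: 2400/400 = 6 ibuprofen plus 90/30 = 3 ketorolac.

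- As the SAP counts: (11×7 + 4×0.3×8)/15 = 86.6/15 = 5.8; difference 5.8 − 5 = 0.8.
- Pooled person-time, which is what a Poisson offset model without covariates estimates: hours = 11×48 + 4×8 = 560; 86.6/560 × 48 = 7.4 per 48 h; difference 2.4.
- Each leaver's own rate carried to 48 h: (77 + 4×0.3×48)/15 = 134.6/15 = 9.0; difference 4.0.

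**2. Equal rates in leavers and completers.** If k of 15 leave at t hours, the arm's mean count falls by (k/15) × (48 − t)/48.

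- k = 2, t = 16: 2/15 × 32/48 = 8.9%.
- k = 5, t = 8: 5/15 × 40/48 = 27.8%.

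So 2 to 5 leavers at 8 to 16 h lower the count by about 9-28%.

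**3. Direction.** Apply the same formula to the active arm: 4 of 15 leaving at 8 h lose 4/15 × 40/48 = 22.2%, so a mean of 5 becomes 3.9. Against a placebo mean of 7 with no withdrawals, a difference of 2.0 would be reported as 3.1. The count can therefore shrink or inflate the contrast.

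**4. Simulation of outcome-linked withdrawal.** 20,000 trials, gamma-Poisson counts (gamma shape 4), means 6 v 4 per 48 h, heaviest users withdrawn at 4 to 16 h. The true difference is 2.0.

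| Withdrawn (placebo v active) | Raw count | Pooled person-time | Mean of subjects' own rates |
|---|---|---|---|
| 0 v 0 | 1.99 | 1.99 | 1.99 |
| 3 v 1 | 0.78 | 1.40 | 1.97 |
| 5 v 1 | 0.00 | 1.08 | 2.00 |
| 6 v 2 | 0.01 | 1.12 | 2.01 |

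Removing exactly the heaviest users is an extreme case. It shows that an offset recovers only part of the difference.

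**5. Time to rescue.** With dosing every 4 h assumed, a first rescue at 9 h is 9 h under SAP 7.9.17 but 1 h after the preceding (third) dose, given at 8 h. The SAP yields one time per subject; up to 12 dose intervals exist (Protocol Table 1). Protocol 4.8 has the CRF capture the time since the last scheduled dose, so the data exist.

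**The case against.** These are secondary endpoints in a 45-subject Phase 2 trial, and Protocol 8.5.3.2 disclaims formal inference on all of them. That limits the weight of the point. It does not remove it: SAP 8.2.2.11 and 8.2.2.12 plan log-rank tests and p-values, and a truncated count misleads as a description too.

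The ANCOVA is the protocol's own choice. This stands, and is a reason to add analyses rather than replace it.

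The SAP handles rescue elsewhere: SAP 7.3.1 replaces pain scores for 4 h after each use, and the proportion using rescue and Kaplan-Meier time to first rescue are also planned. This is correct, so the count should not be presented as the main safeguard for the SPID result.

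Three stronger readings are tempting and are not supported:

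- *The count favours whichever arm has more pain failures, namely placebo.* Protocol 3.3 also withdraws subjects for hypoxia, naloxone use, airway manoeuvres, hypotension and persistent nausea or emesis. Such withdrawals could fall on the fentanyl arms. In addition, a subject withdrawn late after many uses is not scored as a light user.
- *An offset would recover the full 4.0 in the illustration.* It gives 2.4.
- *Time to rescue covers the first dose only.* Follow-up runs to the last pain assessment, so a first rescue after a later dose is an event. What is missing is the clock from the preceding dose.

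**Conclusion.** Both parts hold. The count in SAP 7.9.16 and 8.2.2.12 is not adjusted for time observed (it is adjusted for site and baseline pain), while the protocol mandates a withdrawal linked to rescue need. The documents do not fix the magnitude: differences of 0.8, 2.4 or 4.0 uses come from one set of assumed rates under three ways of treating the same leavers, and the 9-28% loss assumes equal rates and 2 to 5 of 15 leaving at 8 to 16 h. The direction depends on withdrawals by arm and reason, which the documents do not give.

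The time-to-rescue part needs no assumption. The per-dose endpoint and the protocol's per-dose average have no definition, censoring rule or analysis in the SAP. The matter should be corrected before unblinding, but it does not touch the primary analysis.

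**What to change.** **SAP 8.2.2.12.** Keep the ANCOVA on counts. Add a negative binomial model (or Poisson with robust SE) with treatment, site, baseline pain and offset log(hours observed in the window). Because the offset corrects only partly when the heaviest users leave, add a rank-based sensitivity analysis that puts subjects withdrawn for inadequate pain control in the worst rank.

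**SAP 7.9.17 and 8.2.2.11.** Keep the Time 0 analysis. Add time from each dose of investigational product to first rescue before the next dose, censored at the next dose or the last assessment. Summarise it per dose and as the protocol's per-subject average, with any treatment comparison clustered by subject.

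**Rescue definition.** Protocol 3.1 and 4.8 and SAP 2.2 describe the assigned study drug as the primary form of rescue, whereas SAP 7.9.17 identifies rescue from the Concomitant Medications eCRF. Reconcile these passages so that it is clear which uses count as rescue events; otherwise censoring at the next dose could itself be censoring at a rescue.

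**Cost.** SAP wording and a little more analysis on data already collected. The rate model assumes a constant rescue rate within the window.

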7.9.17 Time to First Use of Rescue Medication

Time to first use of rescue medication for pain is defined as the time from Time 0 to the first use of rescue medication. Rescue medications for pain will be identified by the sites on the Concomitant Medications eCRF. If rescue medication for pain is not taken, the time will be censored at the time of the last pain assessment.

7.9.18 Subject's Global Evaluation of Study Drug

Subjects will complete a subject's global evaluation of study drug at the end of the treatment period (Day 3) before discharge from the study site or immediately before Early Withdrawal if a subject discontinues prematurely. The subject will be instructed to score his or her global evaluation of the study treatment on a 5-point categorical scale where 0 = poor, 1 = fair, 2 = good, 3 = very good, and 4 = excellent.

8. STATISTICAL METHODS

All data collected during this study will be presented in subject data listings. All statistical analyses will be performed using SAS® for Windows, version 9.4 or later.

8.1 Summarizing and Tabulating the Collected Data

All data collected will be summarized according to the variable type:

- Continuous data summaries will include number of observations, mean, standard deviation, median, and minimum and maximum values.
- Categorical data summaries will include frequency counts and percentages.

8.1.1 Subject Disposition and Withdrawals

There will be a detailed accounting of all subjects that signed the informed consent to participate in this trial. The following will be summarized by treatment group:

- The number of subjects who signed the informed consent
- The number of subjects who are randomized
- The number of subjects who are randomized and not treated
- The number of randomized and treated
- The number of subjects who completed the treatment phase
- The number of subjects who completed the follow up phase
- The number of subjects who discontinued

Reasons for discontinuation will also be summarized.

In addition, there will also be a listing of all discontinued subjects, which will provide the clinical trial center, treatment group and the specific reason for discontinuation.

8.1.2 Protocol Deviations

Protocol deviations will be identified and classified as minor or major before un-blinding.

Protocol deviations occurring during the clinical trial will be summarized descriptively and also be presented as by-subject listings.

8.1.3 Demographics and Baseline Characteristics

Demographic and baseline characteristics (including age, gender, race, weight, height, BMI, surgery duration, and baseline pain intensity) will be summarized by treatment group and for the overall population by descriptive statistics. No formal statistical analyses will be performed. Medical history, clinical laboratory test results, and urine drug screen, alcohol breathalyzer test, X-ray and podiatric examination assessments will be listed.

The analyses of demographics and baseline characteristics will be conducted for the safety population.

8.1.4 Prior and Concomitant Medications

Prior and concomitant medications will be summarized by treatment group and by the number and percentage of subjects taking each medication. They will also be classified by using the World Health Organization Drug Dictionary Anatomical Therapeutic Chemical classes and preferred terms.

8.1.5 Exposure and Compliance

The exposure to study medication will be summarized by descriptive statistics. As the dose administration is under the control of the study sites, compliance is not expected to be an issue.

8.2 Analysis of Efficacy Data

8.2.1 Primary Endpoint

The primary efficacy endpoint is the NRS summed pain intensity difference over 0 to 48 hours after Time 0 (NRS SPID-48). The formula for SPID-48 calculation is presented in [Section 7.9.7](#). The primary variable will be analyzed using an analysis of covariance (ANCOVA) model, which will include treatment and site as main effects and baseline pain intensity as the covariate. The least square (LS) mean, standard error (SE) and 95% confidence interval (CI) for each treatment group will be estimated. In addition, the mean (LS mean) difference between each treatment and placebo, SE, p-value and the associated 95% CI will also be computed. Descriptive summaries (including mean, SD, median, minimum and maximum) will also be presented by treatment group. Missing values for pain intensity will NOT be imputed in the primary analysis.

8.2.2 Secondary Endpoints

Analysis of the secondary endpoints will be summarized according to the variable type. The details are presented in the following sections.

8.2.2.1 NRS SPID over 0 to 24 hours (NRS SPID-24), over 0 to 8 hours (NRS SPID-8), and over 0 to hours (NRS SPID-4) after Time 0

NRS SPID-24, SPID-8 and SPID-4 would be calculated using the formula specified in [Section 7.9.7](#). Similar methods used for analysis of the primary endpoint will be assessed differences between the treatment groups in these metrics.

8.2.2.2 Total pain relief (TOTPAR) over 0 to 48 hours (TOTPAR-48), over 0 to 24 hours (TOTPAR-24), over 0 to 8 hours (TOTPAR-8), over 0 to 4 hours (TOTPAR-4)

TOTPAR over 0-48, 0-24, 0-8 and 0-4 hours will be calculated using the formula specified in [Section 7.9.9](#). The differences in TOTPAR between the treatment groups and placebo will be compared using an analysis of covariance (ANCOVA) model, which will include treatment and site as main effects and baseline pain intensity as the covariate. The last square (LS) mean, standard error (SE) and 95% confidence interval (CI) for each treatment group will be estimated. In addition, the mean (LS mean) difference between each treatment and placebo, SE, p-value and the associated 95% CI will also be computed. Descriptive summaries (including mean, SD, median, minimum and maximum) will also be presented by treatment group.

8.2.2.3 Subject's global evaluation of study drug

Subject's global evaluation of study drug will be analyzed using a proportional odds model (an extension of the logistic regression). This method allows for an ordinal response variable with more than two categories. This model will include factors site, treatment and baseline pain intensity.

8.2.2.4 Time to onset of analgesia (measured as time to perceptible pain relief confirmed by meaningful pain relief using the 2-stopwatch method)

Time to onset of analgesia will be summarized using Kaplan-Meier methods. The definition and censoring rules are described in [Section 7.9.11](#). Treatments will be compared to placebo using a log-rank test which will compare the survival distributions of the treatments.

8.2.2.5 Pain relief score on a 5-point categorical scale at each scheduled time point after Time 0

The differences in pain relief between the treatment groups and placebo will be compared using a proportional odds model (an extension of logistic regression model) which allows for an ordinal response variable with more than two categories. This model will include factors site, treatment and baseline pain intensity.

In addition, the pain relief scores at each time point will also be summarized descriptive in tables and also presented as by-subject listings.

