2.4.2 Method of Treatment Assignment, Randomization Ratio, and Stratification

Subjects who have met all of the inclusion and none of the exclusion criteria, have provided written informed consent, and have experienced a pain intensity rating of ≥ 4 on the NRS during the 9-hour period after discontinuation of the anesthetic block are eligible to be enrolled in the study. They will be randomly assigned to 1 of 3 treatment groups: Fentanyl Sublingual Spray 100 µg q4h, 200 µg

q4h, or matching placebo. The randomization will be stratified by center and use mixed blocks with a 1:1:1 ratio to ensure even distribution of subjects across each treatment group in every site.

In addition, an enrollment anticipated at each of the sites in the following:

- [REDACTED] (PI: Dr. [REDACTED]) = approximately 30 subjects
- [REDACTED] (PI: Dr. [REDACTED]) = approximately 15 subjects

The actual randomization assignment will be made through an Interactive Web Based System (IWRS) called [REDACTED]. [REDACTED] is a Secure Socket Layer (SSL) web portal that allows 24/7 access to clinical trial information. Authorization is based on approved access control list (ACL) that determines a user's access to the site. The [REDACTED], who is not otherwise involved with the study, is responsible for the implementation and maintenance of [REDACTED]. Each user will be trained in how to use the website. A [REDACTED] user manual will be supplied to all study personnel with instructions on using the website.

The Randomization/Supply module of [REDACTED] allows authorized users to request randomization (Site Personnel only) into the trial. The detailed description and instructions are included in the [REDACTED] user manual. [REDACTED] has further documentation and validation of [REDACTED] specifically with regards to preserving the blinding of this study.

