4. SAMPLE SIZE DETERMINATION AND RATIONALE, STATISTICAL POWER, AND SIGNIFICANCE LEVEL

A total of 45 subjects are planned to be enrolled for the study. A sample size of 15 subjects per treatment group will provide $\geq 80\%$ power to detect a minimal standardized effect size of 0.5 between the 100 μg q4h, 200 μg q4h active treatment arms, and placebo in NRS SPID-48 using a 3-group analysis of covariance (ANCOVA) with baseline NRS score as the covariate with a 0.05 two-sided significance level (EAST v6).

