7.5 Multiple Clinical Trials

This is a multi-center clinical trial with two sites.

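### The five log-rank tests name no site stratum, although randomisation is stratified by site and every other SAP efficacy model includes site: a cheap, low-severity improvement

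*SAP*

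**What the plan says.** SAP 2.4.2 on randomisation: "The randomization will be stratified by center and use mixed blocks with a 1:1:1 ratio". SAP 7.5: "This is a multi-center clinical trial with two sites". SAP 2.4.2 anticipates "approximately 30 subjects" at one site and "approximately 15 subjects" at the other.

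The primary analysis (SAP 8.2.1) is an ANCOVA "which will include treatment and site as main effects and baseline pain intensity as the covariate". Site also appears in:

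- the ANCOVAs for TOTPAR, total rescue use, PID and pain intensity, and, by reference to the primary method, SPID-24, SPID-8 and SPID-4;
- the proportional odds models for global evaluation, pain relief and peak pain relief;
- the logistic model for the proportion using rescue;
- the multiple-imputation model and its ANCOVA (SAP 7.4.2).

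Time to onset of analgesia (8.2.2.4), time to peak relief (8.2.2.7), time to first perceptible relief (8.2.2.8), time to meaningful relief (8.2.2.9) and time to first rescue (8.2.2.11) are handled differently. Each gets Kaplan-Meier estimates and this sentence: "Treatments will be compared to placebo using a log-rank test which will compare the survival distributions of the treatments". None names a stratum or a covariate.

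**The concern.** An analysis should normally respect the factor used to stratify randomisation, and the SAP does so everywhere except in these five sections. The contrast is sharpest for rescue: whether a subject used rescue is adjusted for site (8.2.2.10), but when rescue was first used is not (8.2.2.11).

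Stratified randomisation balances the arms within each site. If event times differ between sites, an unstratified log-rank test leaves that variation in the comparison, becomes conservative and loses power. Onset of analgesia and time to rescue are both named as secondary objectives in the protocol synopsis and SAP 2.1 (protocol 2.2 lists onset only). Each comparison has about 30 subjects, so there is little power to spare.

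**Working it through.** **Is the gap filled elsewhere?** No. SAP 7.7 names site and baseline pain as covariates for the primary endpoint only. Protocol 8.5.3.2 asks for Kaplan-Meier methods and leaves details to the SAP. The SAP does not say unstratified, but a log-rank test with no stated strata is unstratified by default.

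**Is there a plan figure to reproduce?** No. The documents give no event count, hazard ratio or power for any of these endpoints. The power statement in SAP section 4 concerns SPID-48 and cannot be carried over.

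**Inputs from the documents**
- "A total of 45 subjects are planned to be enrolled for the study"; "A sample size of 15 subjects per treatment group will provide" the stated power, that is 15 per arm.
- At 1:1:1, the larger site gives 30/3 = 10 per arm and the smaller 15/3 = 5 per arm. One active arm v placebo is therefore 10+10 and 5+5, or 30 subjects.
- Two-sided 0.05, stated for the primary endpoint and borrowed here.

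**Assumptions (not in the documents)**
- Exponential event times, proportional hazards, treatment HR 2.5 or 3, between-site HR 1 to 5.

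**Formulas**
- Unstratified: Z = U/√V, where U sums, over events, the active-arm indicator minus p, V sums p(1−p), and p is the active-arm share of those at risk at both sites together.
- Stratified: compute U and V within each site, then Z = (U₁+U₂)/√(V₁+V₂). Reject if |Z| > 1.96.

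**Anchor without a site effect** (Schoenfeld, 30 events): power = Φ(√(30/4)·ln HR − 1.96).
- HR 3: 2.739 × 1.099 − 1.96 = 1.05, power 85%.
- HR 2.5: 2.739 × 0.916 − 1.96 = 0.55, power 71%.

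The simulated values below (80% and 66% unstratified) are somewhat lower.

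**Simulation**, 40,000 trials per scenario (standard error about 0.2 points near 77%), every subject observed to the event. Cells are unstratified v stratified.

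| Between-site HR | Power, treatment HR 3 | Power, treatment HR 2.5 | Rejection with no treatment effect |
|---|---|---|---|
| 1 | 80.3% v 77.0% | 65.7% v 62.5% | 6.1% v 6.0% |
| 2 | 76.2% v 76.9% | 60.4% v 62.1% | 5.1% v 5.9% |
| 3 | 70.7% v 77.1% | 55.1% v 62.8% | 4.2% v 6.0% |
| 5 | 63.7% v 77.0% | 47.2% v 62.1% | 3.0% v 5.6% |

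**Effect of follow-up**
- 4 hours, assumed placebo hazard 0.5 per hour at the larger site, treatment HR 3: 80% v 77% at site HR 1, 76% v 77% at 2, 70% v 77% at 3, 66% v 77% at 4. The unstratified null rejection rate is 4.0% at site HR 3 and 3.6% at 4.
- Heavier censoring (4 hours, control hazard 0.25 per hour), treatment HR 3: 75.6% v 73.4% at site HR 1, 75.5% v 74.2% at 1.5, 73.4% v 74.5% at 2, 67.8% v 74.4% at 3. The two tests break even between site HR 1.5 and 2.

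**Reading the results**, treatment HR 3, no censoring: stratifying costs 80.3 − 77.0 = 3.3 points if the sites are alike. It gains 76.9 − 76.2 = 0.7 at site HR 2, 77.1 − 70.7 = 6.4 at 3, and 77.0 − 63.7 = 13.3 at 5.

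**The case against.** The case against acting has several parts.

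- **The harm is conditional.** A reader might infer that an unstratified log-rank test after stratified randomisation is conservative and underpowered as a rule. The figures do not support that. With no site effect the SAP's test is about 3 points more powerful, and at a between-site HR of 2 the difference is only 1 to 2 points. This stands.
- **No large site effect is documented.** The protocol standardises the nerve block, the time the infusion stops, the entry pain threshold, and the rescue agents and intervals. Differences remain possible: staff train subjects on the stopwatches, and rescue is given as needed, with subjects only encouraged to wait an hour. But a threefold ratio is an assumption. This stands.
- **Part of the power gap reflects test size.** At site HR 3 the stratified test rejects 6.0% under the null and the unstratified 4.2%, so the raw comparison flatters stratification somewhat. This stands. The excess over 5% is small-sample behaviour that the unstratified test shares when sites are alike (6.1%).
- **A 4-hour horizon suits only the stopwatch endpoints.** Time to rescue and time to peak relief can run to 48 hours. This does not change the result, because the pattern is the same when every subject is followed to the event.
- **Little depends on these p-values.** The endpoints are secondary, in a 45-subject Phase 2 trial, and protocol 8.5.3.2 disclaims formal inference on them. This stands and limits the severity. The SAP nevertheless prescribes the tests.
- **Stratifying by site does not fully align the analyses.** The other models also adjust for baseline pain. This stands.

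**Conclusion.** The inconsistency in the SAP is certain: five log-rank tests name no stratum, while randomisation and every other SAP efficacy model use site. Its consequence is conditional and modest. Under the assumptions above, the unstratified test loses about 1 to 2 points of power at a between-site HR of 2, 6 to 8 at 3 and 13 to 15 at 5. With no site effect it is about 3 points better.

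A reader might go further and infer that the tests are invalid or would produce false positives. That does not follow: the unstratified rejection rate under the null is no higher than the stratified one beyond simulation error, and it falls as site becomes more prognostic. Nor do the documents show that power will be lost in this trial, since they give no site effect. This is a low-severity, cheap improvement, and no primary conclusion depends on it.

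**What to change.** In SAP 8.2.2.4, 8.2.2.7, 8.2.2.8, 8.2.2.9 and 8.2.2.11, specify a log-rank test stratified by site for each active arm against placebo, and keep the unstratified test as a sensitivity analysis. Do this before unblinding, so that no one later chooses between two defensible p-values. If alignment with the other models on baseline pain is also wanted, a Cox model stratified by site with baseline pain as covariate could be added as supportive.

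The edit is a few words per section. The statistical cost is about 3 points of power if the sites do not differ, and a null rejection rate of about 5.5 to 6% in samples this small, which the unstratified test shares when sites do not differ.
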